3.2 Medical Devices and Indication

The WATCHMAN (Atritech, Boston Scientific, Natick, MA, USA) LAAC technology consists of the Access System (Access Sheath and Dilator) and Delivery System (Delivery Catheter and WATCHMAN Device). The Access System and Delivery System permit Device placement in the left atrial appendage (LAA) via femoral venous access and inter-atrial septum crossing into the left atrium. WATCHMAN device is a self-expanding nitinol structure with a porous covering on the proximal face. The device is constrained within the Delivery System until deployment in the LAA. The Device is available in 5 sizes from 21 to 33 mm. The new generation Watchman FLX has a shorter device length and a less taper angle to simplify implantation and to fit a wider range of patients. Furthermore, the frame of the new device is designed to enhance sealing within the left atrial appendage.

The AMPLATZER Amulet (St. Jude Medical-Abbott) is a self-expanding device made of nitinol that has a distal lobe and a proximal disc, connected by an articulated waist. The device lobe has six to 10 pairs of stabilising wires and is meant to be implanted in the proximal 10-15 mm of the left atrial appendage (LAA), whereas the device disc is intended to cover the ostium at the left atrial side. The proximal female screw is recessed to minimise thrombus formation on the disc and potentially facilitate re-attachment of the device to the pusher screw. The lobe sizes range from 16 to 34 mm.

3.3 Preclinical Evidence

Not applicable, all the devices used in this study have been previously approved for use in humans in the context of LAAC.

3.4 Clinical Evidence to Date

Addition to the two randomized clinical trials previous reported, there are many prospective and retrospective study reported both for the Watchman that for the Amulet the safety and efficacy of the LAAC procedure. In a recent meta-analysis, Xu et al.²⁰ reported the data of 2779 patients underwent to LAAC with the two devices. They reported a rate of stroke about 1.2/100 person-year, with a rate of major bleeding (that is the most important procedure adverse event) of 2.6%.

3.5 Explanation for choice of comparator

The two devices selected for this study are the two most used in Europe. No previous randomized studies are reported about the comparison between the two devices in terms of safety and efficacy and between the two evaluation techniques (CCTA and TEE).

3.6 Risks / Benefits

Patients will not be exposed to any adjunctive procedural hazard by participating into the present study because LAAC is a clinically-indicated procedure in this specific patient population. As previously described, AF patients are at risk of cardioembolic stroke. So it is mandatory to prescribe an anticoagulant therapy if AF is detected. The most important risk of this therapy is related to bleeding events. On the other side, the interventional procedure itself exposes the patient to the risk of possible complications, sometimes also severe such as migration/embolization of the device or major bleeding (pericardial effusion or pericardial tamponade) requiring an intervention. However, as reported in literature, these events are rare and their incidence is lower than the incidence of stroke in AF patients or as compared to the risk of bleeding complications inpatients taking (N)OAC.

Patients are to receive, as per current standard of care, CCTA before LAAC and TEE both during the procedure and at follow-up. As multiple reports²¹ exist indicating that CCTA improves proper sizing of the LAAC device and is useful to detect LAA thrombus before LAAC, nowadays many centres across the world including ours, recommend CCTA before (and frequently after) the planned intervention.

The only added risk in this study for the participating patients is represented by the routine performance of two CCTAs undertaken after the procedure, since these diagnostic assessments are, at least partially, study-specific procedures. As previously described, we will use the CCTA performed 45 days after procedure as primary endpoint measure since it is more sensitive in detecting LAA leaks after LAAC as compared to TEE¹⁵, and CCTA at 13 months after procedure as secondary endpoint measure to better characterize the natural history of peridevice leak(s). Replacing TEE with CCTA is also desirable for patients as it is non-invasive and less time consuming.

Unlike TEE however, CCTA is associated to ionizing radiation to patients and contrast exposure. With the most recent technology and new acquisition protocols, the radiation dose for each exam is lower than 5 mSv. In a recent publication,¹⁹ the median radiation dose (range) for the dual-phase protocol of patients submitted to a CCTA for LAA evaluation prior LAAC was **3.5 mSv** (2.1–5.2 mSv), with a dose-length product (DLP) of 251 mGy cm (150–374). However taking all CCTAs performed before the index procedure, after 45 days and after 13±1 months into account, the total dose per year is projected to exceed the limit of 5mSv yearly limit and so, as required by Ordinance on Clinical Trials in Human Research of 20 September 2013 (Status as of 1 January 2018- Sect.2 Art. 28), an additional submission to the FOPH will be accomplished.

Since patients with reduced kidney function (i.e. CrCl< 30 ml/h/kg) are excluded, we believe additional contrast exposure will not result in additional kidney injury in our patient population.

3.7 Justification of choice of study population

High bleeding risk (HBR) patients are the ones that most benefit from the LAAC, as it suppresses the need for chronic anticoagulation therapy.

4. STUDY OBJECTIVES

4.1 Overall Objective

The purpose of this study is to compare the efficacy and safety of the two devices for the LAAC.

4.2 Primary Objective

The main objective is to evaluate the feasibility and the efficacy of the devices in terms of LAA complete occlusion with a non-invasive imaging technique such as CCTA.

4.3 Secondary Objectives

Other secondary objectives will include the incidence of adverse clinical events in the two groups, a comparison between the two devices in terms of procedure feasibility, LAA patency and device thrombus over time as assessed with both 45-day and 13-month CCTA and with 45 day TEE. Furthermore, a secondary objective of the study will be the comparison between TEE and CCTA with respect to LAA patency and device thrombus.

4.4 Safety Objectives

Safety objective is to show that there is no significant difference in terms of procedure complications up to 48 hours from randomization across the two groups.

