Study Product / Intervention:	
The WATCHMAN (Atritech, Boston Scientific, Natick, MA, USA) LAAC technology consists of the Access System (Access Sheath and Dilator) and Delivery System (Delivery Catheter and WATCHMAN Device). The Access System and Delivery System permit Device placement in the left atrial appendage (LAA) via femoral venous access and inter-atrial septum crossing into the left atrium. WATCHMAN device is a self-expanding nitinol structure with a porous covering on the proximal face. The device is constrained within the Delivery System until deployment in the LAA. The Device is available in 5 sizes from 21 to 33 mm. The new generation Watchman FLX has a shorter device length and a less taper angle to simplify implantation and to fit a wider range of patients. Furthermore, the frame of the new device is designed to enhance sealing within the left atrial appendage.
 
The AMPLATZER Amulet (St. Jude Medical-Abbott) is a self-expanding device made of nitinol that has a distal lobe and a proximal disc, connected by an articulated waist. The device lobe has six to 10 pairs of stabilising wires and is meant to be implanted in the proximal 10-15 mm of the left atrial appendage (LAA), whereas the device disc is intended to cover the ostium at the left atrial side. The proximal female screw is recessed to minimise thrombus formation on the disc and potentially facilitate re-attachment of the device to the pusher screw. The lobe sizes range from 16 to 34 mm.

Number of Participants with Rationale:	
Total number of patients with primary endpoint assessment: 200 100 patients in the Watchman/FLX group 100 patients in the Amplatzer Amulet group Sample size is calculated to state superiority of Amplatzer Amulet compared with Watchman/FLX

Study Duration:	8 years
Study Schedule:	February 2018 February 2026

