5.3 Procedure-related complications¹

Procedure related complications are defined as adverse clinical events occurring during the procedure or within 7 days after. In particular, the following complications will be adjudicated by the Clinical Events Committee (CEC) : death, TIA/stroke, systemic and pulmonary thromboembolic event, pericardial effusion, cardiac tamponade, air embolism, bleedings vascular access-related complications, epicardial or minimal invasive surgical access-related complications, device complications and acute renal injury. Any events potentially related to the above complications ("adverse events of special interests" [AESI], see the definition in the section 11) should be reported into the ecrf.

¹For the definitions of endpoint and adverse clinical events see the Appendix 1.

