6.2 Randomization

Balanced (1:1) randomization will be performed via a web-based interactive randomization system (ICE-Advice Pharma), based on a computer-generated random sequence with a random block size stratified according to site and allocation to either Amulet Amplatzer device or Watchman/FLX. In the event that the patient is randomized to the Watchman/FLX arm, the operator will be able to choose, on the basis of clinical reasons, if to implant Watchman or the new generation Watchman FLX (if available in the center). Randomization will occur as close as possible to but always before the procedure and once the patient is judged eligible and the informed consent has been signed.

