11.1 Definitions

An **Adverse Event (AE)** is any untoward medical occurrence in a patient or a clinical investigation participant administered a pharmaceutical/device product and which does not necessarily have a causal relationship with the study procedure. An AE can therefore be any unfavourable and unintended sign (including an abnormal laboratory finding), symptom, or disease temporally associated with the use of a device (investigational) product, whether or not related to the device (investigational) product. [ICH E6 1.2]

The AESI are the clinical endpoints of the study (see the list and/or any AEs potentially related to them: overall and CV death, cerebrovascular events (including possible events like fall, syncope, headaches, blurred vision, etc.), cardiovascular events (including possible events like hypotension, myocardial infarction, chest pain, unstable angina), bleeding events (including anemization without overt bleeding); procedure-related complications (any AE occurred within 7 days after LAAC and potentially related to the procedure). All the AESI will be evaluated by the CEC and adjudicated as clinical endpoints of the study according the definitions mentioned in Appendix 1.

A **Serious Adverse Event (SAE)** is classified as any untoward medical occurrence that:

- Results in death,
- Is life-threatening,
- Requires in-patient hospitalization or prolongation of existing hospitalisation,
- Results in persistent or significant disability/incapacity.

In addition, important medical events that may not be immediately life-threatening or result in death, or require hospitalisation, but may jeopardise the patient or may require intervention to prevent one of the other outcomes listed above should also usually be considered serious. [ICH E2A]

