12.1 Hypothesis

Null hypothesis A (H_{0A}): ACP Amulet is superior in terms of complete LAA occlusion to WATCHMAN/FLX device and is more feasibility.

Null hypothesis B (H_{0B}): there is no difference between ACP Amulet and WATCHMAN/FLX in terms safety, feasibility and LAA patency.

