3.2 Data validation

Before locking, the data will be checked for completeness using e.g. missing tables functions. The plausibility of the primary and secondary outcomes will be checked using outlier analyses and histograms, and will be queried if they are outside the expected range, including dates of events. Only events occurring after the implantation (attempt) of the LAAC device will be analysed, in case no LAAC procedure was started the randomization date will be used instead.

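### The safety objective treats a non-significant difference as the goal, with no margin or interval, and its 48-hour window from randomisation conflicts with the 7-day definition of procedure-related complications

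*Combined protocol and SAP*

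**What the plan says.** Protocol 4.4: "Safety objective is to show that there is no significant difference in terms of procedure complications up to 48 hours from randomization" between the two groups. Protocol 12.1 has the same idea in its null hypothesis B: "there is no difference between ACP Amulet and WATCHMAN/FLX in terms safety, feasibility and LAA patency".

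The endpoint is defined elsewhere with a different window. Protocol 5.3: "Procedure related complications are defined as adverse clinical events occurring during the procedure or within 7 days after", with adjudication by the Clinical Events Committee (CEC). Protocol 11.1 again describes these complications as "any AE occurred within 7 days after LAAC and potentially related to the procedure". SAP 3.2 fixes the start of counting: "Only events occurring after the implantation (attempt) of the LAAC device will be analysed", falling back on the randomisation date only if no procedure was started. Protocol 6.2 separates the two starting points: "Randomization will occur as close as possible to but always before the procedure".

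Protocol 5.5 adds a further set of safety outcomes (bleeding and net adverse clinical events), assessed at 48 hours or earlier discharge and at 45 days.

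On size and analysis, the synopsis plans "100 patients in the Watchman/FLX group 100 patients in the Amplatzer Amulet group". Protocol 12.2 and SAP 2.3 justify this from the primary endpoint alone. SAP 5.5, Table 2 (procedural characteristics) lists the periprocedural complications by arm with counts, percentages and a p-value, and its footnote names Fisher's test for these.

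**The concern.** A test that fails to reject says little unless the trial could have detected a difference that matters. Taking a non-significant result as the aim reverses the incentive: fewer events and lower power make the aim easier to reach. An equal-safety statement needs either a margin set in advance or, at the least, an interval showing which differences the data exclude. Section 4.4 has neither, and the SAP table for these complications does not supply the interval.

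The window adds a second problem. A team following 4.4 and a team following 5.3 would count different events over different periods from different starting points. Both could claim to follow the plan.

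At stake is whether the report of a two-device comparison could state that its safety objective was met on data that are compatible with a clinically important excess in one arm.

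**Working it through.** **Inputs.** 100 per arm (synopsis); 5% significance level (SAP 4.1), taken as two-sided because the documents do not say; Fisher's test (footnote to SAP 5.5, Table 2), with uncorrected chi-square alongside because protocol 12.4 and SAP 4.1 allow either. The control rate is an assumption. Protocol 3.4 quotes 2.6%, but for major bleeding only. Protocol 3.1 reports procedural success in 53 of 56 patients, so 3/56 = 5.4% without it; that series is small, mostly used the older device, and counts technical failures too. I therefore show 2.6%, 5% and 10%.

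**The plan's own figure.** For 50% against 30% on the primary endpoint, with pooled proportion p̄ = 0.40:

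z = (|p₁ − p₂|√n − 1.96√(2p̄(1 − p̄))) / √(p₁(1 − p₁) + p₂(1 − p₂)) = (2.000 − 1.358)/0.678 = 0.947

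This gives 82.8% power. Exact enumeration gives 83.2% with chi-square and 79.2% with Fisher. The stated power above 80% is reproduced for chi-square. It has no bearing on safety, for which the plan gives no power.

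**Chance of a non-significant result when the true rates differ.** Method: sum the product of the two binomial probabilities (n = 100 each) over all pairs of counts with p ≥ 0.05.

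| Assumed control rate | Doubling: Fisher / chi-square | Tripling: Fisher / chi-square |
|---|---|---|
| 2.6% | 93% / 86% | 74% / 63% |
| 5% | 81% / 73% | 41% / 32% |
| 10% | 56% / 48% | 7% / 4% |

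The control rate at which a tripling is missed exactly half the time is about 4.3% with Fisher and 3.5% with chi-square.

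**Observed counts, which need no assumed rate.**

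- 10/100 against 3/100: Fisher p = 0.08, so not significant. Wilson limits are 5.5% to 17.4% and 1.0% to 8.5%. The Newcombe interval for the 7-point difference is 7 − √(4.48² + 5.45²) to 7 + √(7.44² + 1.97²), or about −0.1 to +14.7 points. Uncorrected chi-square on the same counts gives z = 0.07/√(0.065 × 0.935 × 2/100) = 2.01, just past 1.96. Whether the objective is met here would turn on the choice of test.
- 3/100 against 3/100: Newcombe half-width √(1.97² + 5.45²) = 5.8, so −5.8 to +5.8 points. Identical counts still leave a difference of more than 5 points in either direction compatible with the data.

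**The windows side by side.**

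| Place | Starts | Ends |
|---|---|---|
| Protocol 4.4 | randomisation | 48 hours later |
| Protocol 5.3 | procedure | 7 days after |
| Protocol 11.1 | LAAC | 7 days after |
| SAP 3.2 | implantation attempt | not set there |
| SAP 6.5 | not set there | includes a 7-day tabulation |

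Only 4.4 starts at randomisation when a procedure took place, and only 4.4 stops procedure complications at 48 hours.

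**The case against.** Five points can be made in the plan's defence.

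- **No decision rule is attached to 4.4.** True: the documents nowhere say that p above 0.05 counts as success. That reading is an inference from an objective worded as showing no significant difference. But nothing in the plan blocks it either.
- **The SAP already moves away from this wording.** SAP 2.4 leaves safety out of its hypotheses, SAP 3.2 counts from the implantation attempt, and SAP 6.5 includes a 7-day tabulation. This stands, and it makes the repair largely one of bringing the protocol into line.
- **Intervals are not absent from the SAP.** SAP 5.7, Table 4 gives differences with 95% confidence intervals for death, stroke, embolism, device embolization and bleeding at 45 days. This stands for those outcomes. The periprocedural block in SAP 5.5, Table 2 has p-values only.
- **A tripling need not be missed.** A reader might infer that 100 per arm would usually fail to detect a tripling of complications. The documents do not support that without a condition. The 2.6% rate is major bleeding alone, whereas the 5.3 list also covers effusion, vascular access, device and renal events and has no combined rate. At 5% a tripling is missed 41% of the time and at 10% only 7%.
- **The 48-hour clock should not run out before implantation.** A reader might infer that it could, because the schedule puts randomisation in an enrolment column that reaches back 90 days. That column covers the whole screening period. Protocol 2.4 places consent on the day of the procedure or the day before, randomisation follows consent, and 6.2 keeps it close to the procedure. No maximum gap is set, but the documents read together point to about a day at most. The mismatch in length and starting point remains.

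**Conclusion.** The objective in 4.4 is wrong as written. It makes absence of significance the aim, gives no margin or expected rate, and is paired with a table of p-values alone. With 100 per arm, Fisher's test would miss a doubling 93% of the time at a 2.6% control rate, 81% at 5% and 56% at 10%. It would miss a tripling more often than not only below a control rate of about 4.3%. These figures rest on assumed control rates, a two-sided 5% level and full follow-up of both arms. The logical point and the two observed-count examples do not depend on an assumed rate.

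The conflict of windows is a matter of text and needs no assumption: 48 hours from randomisation cannot be reconciled with the procedure plus 7 days, or with counting from the implantation attempt. How far the choice of window would change the result cannot be judged from the documents.

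This concerns a non-primary objective and does not affect the primary analysis.

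**What to change.** 1. Reword protocol 4.4: the aim is to estimate the between-arm risk difference, with 95% confidence interval, in CEC-adjudicated procedure-related complications as defined in 5.3, counted from the implantation attempt as in SAP 3.2.
2. State there that a non-significant test will not be taken as evidence of equal safety.
3. Keep the 48-hour/discharge outcomes of 5.5 as separately labelled outcomes, so that they are not confused with the 5.3 endpoint.
4. Add the risk difference and its 95% confidence interval to the periprocedural block of SAP 5.5, Table 2.
5. Remove safety from null hypothesis B in protocol 12.1, to match SAP 2.4.

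The cost is wording and one table column, with no added patients, visits or data. The price is a more modest safety claim: at an assumed 2.6% in both arms the interval would run about 1.96√(2 × 0.026 × 0.974/100) = 4.4 points either side, and at 5% about 6.0 points. A formal non-inferiority claim would need a justified margin and probably a larger trial. As an illustration, with equal rates of 5%, one-sided 2.5% and 80% power, a 5-point margin needs 299 per arm.

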5. STUDY OUTCOMES

5.1 Primary Outcome

The study primary endpoint is the composite of LAA patency at 45 day evaluated with CCTA or the crossover from one device to the other device based on morphological/anatomical considerations during device implantation.

Post-intervention LAA patency will also be assessed via TEE based on the more conservative criterion of residual flow ≥ 3 mm.

5.2 Secondary Outcomes

Secondary end-points include¹:

- LAA patency (arterial and/or venous phase) at 45-day and 13-month CCTA in the per protocol and as treated populations
- All cause of death, stroke, systemic or pulmonary embolism and spontaneous MI
- Cardiovascular death
- Ischemic stroke
- Haemorrhagic stroke
- Bleeding events according to the BARC classification at each follow up.
- Procedure-related complications²
- Rate of patients on (N)OAC at 45 days and 6 months
- Device related thrombosis (DRT) at 45 day TEE/CCTA and 13-month CCTA in the per protocol and as treated populations
- Feasibility outcome (number of device implantation attempts, total time procedure, x-ray dose and total contrast dose used in the procedure)
- LAA patency at 45 day TEE in the per protocol and as treated populations

Adverse clinical events will be assessed at up to 48 hours or discharge whichever comes first, at 45 days, and yearly.

¹ For the definitions of endpoint and adverse clinical events see the Appendix 1.

²As defined in 5.3.

5.3 Procedure-related complications¹

Procedure related complications are defined as adverse clinical events occurring during the procedure or within 7 days after. In particular, the following complications will be adjudicated by the Clinical Events Committee (CEC) : death, TIA/stroke, systemic and pulmonary thromboembolic event, pericardial effusion, cardiac tamponade, air embolism, bleedings vascular access-related complications, epicardial or minimal invasive surgical access-related complications, device complications and acute renal injury. Any events potentially related to the above complications ("adverse events of special interests" [AESI], see the definition in the section 11) should be reported into the ecrf.

¹For the definitions of endpoint and adverse clinical events see the Appendix 1.

